observed in 0.6%, 0.5% and 0.4% of patients receiving placebo, 5 mg, and 10 mg twice daily, respectively. One case of drug-induced liver injury was reported in a patient treated with Tofacitinib 10 mg twice daily for approximately 2.5 months. The patient developed symptomatic elevations of AST and ALT greater than 3x ULN and bilirubin elevations greater than 2x ULN, which required hospitalizations and a liver biopsy.

- Lipid elevations: In the controlled clinical trials, dose-related elevations in lipid parameters (total cholesterol, LDL cholesterol, HDL cholesterol, triglycerides) were observed at one month of exposure and remained stable thereafter. Changes in lipid parameters during the first 3 months of exposure in the controlled clinical trials are summarized: Mean LDL cholesterol increased by 15% in the Tofacitinib 5 mg twice daily arm and 19% in the Tofacitinib 10 mg twice daily arm. Mean HDL cholesterol increased by 10% in the Tofacitinib 5 mg twice daily arm and 12% in the Tofacitinib 10 mg twice daily arm. Mean LDL/HDL ratios were essentially unchanged in Tofacitinib-treated patients. In a controlled clinical trial, elevations in LDL cholesterol and ApoB decreased to pretreatment levels in response to statin therapy. In the long-term safety population, elevations in lipid parameters remained consistent with what was seen in the controlled clinical trials.
- Serum creatinine elevations: In the controlled clinical trials, dose-related elevations in serum creatinine were observed with Tofacitinib treatment. The mean increase in serum creatinine was <0.1 mg/dL in the 12-month pooled safety analysis; however, with increasing duration of exposure in the long-term extensions, up to 2% of patients were discontinued from Tofacitinib treatment due to the protocol-specified discontinuation criterion of an increase in creatinine by more than 50% of baseline. The clinical significance of the observed serum creatinine elevations is unknown.
- Other adverse reactions: The following occurred in at least 2% or more of patients and at least 1% greater than that observed in patients on placebo:

	Tofacitinib 5 mg Twice Daily	Tofacitinib 10 mg Twice Daily*	Placebo			
Preferred Term	N = 1336 (%)	N = 1349 (%)	N = 809 (%)			
Diarrhea	4.0	2.9	2.3			
Nasopharyngitis	3.8	2.8	2.8			
Upper respiratory tract infection	4.5	3.8	3.3			
Headache	4.3	3.4	2.1			
Hypertension	1.6	2.3	1.1			
N reflects randomized and treated patients from the seven clinical trials						

- Adverse reactions occurring in controlled and open-label extension studies include:
 - o Blood and lymphatic system disorders: Anemia
 - Infections and infestations: Diverticulitis
 - Metabolism and nutrition disorders: Dehydration
 - Psychiatric disorders: Insomnia
 - Nervous system disorders: Paresthesia
 - o Respiratory, thoracic and mediastinal disorders: Dyspnea, cough, sinus congestion
 - Gastrointestinal disorders: Abdominal pain, dyspepsia, vomiting, gastritis, nausea
 - Hepatobiliary disorders: Hepatic steatosis
 - O Skin and subcutaneous tissue disorders: Rash, erythema, pruritus
 - Musculoskeletal, connective tissue and bone disorders: Musculoskeletal pain, arthralgia, tendonitis, joint swelling

- Neoplasms benign, malignant and unspecified (including cysts and polyps): Non-melanoma skin cancers
- o General disorders and administration site conditions: Pyrexia, fatigue, peripheral edema
- Pregnancy and Teratogenic effects: Pregnancy Category C. Pregnant and breastfeeding women will not be included in this trial.

b. Potential Benefits to Subjects

The purpose of this trial is to determine if Tofacitinib is an effective therapy in sarcoidosis. If this therapy is effective, subjects may see a symptomatic improvement and a reduction in corticosteroid requirement. Subjects who meet the primary endpoint will go on to a one-year extension where they will be given the study drug free of cost.

12. Resources Available

This study involves RNA extraction and RNA sequencing, which requires special resources through the Gene Profiling Shared Resource (GPSR). [name] is the director of the GPSR and will be assisting with this study.

13. Drugs or Devices

We will follow the applicable Research Pharmacy policies and procedures and provide Research Pharmacy with a pharmacy manual for the study.

References

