This is a 16-week open-label, interventional, proof of concept, hypothesis-generating study. This study will enroll five subjects over the course of two years. Patients recruited for this study must have histologically proven sarcoidosis, evidence of pulmonary disease on chest imaging, and an FVC >50%. They must require a stable dose (defined by 4 weeks or more) of prednisone at least 15 mg/day or equivalent corticosteroid prior to enrollment in the study. The prednisone dose cannot exceed 30 mg/day. The above criteria should insure that this is a relatively uniform group of subjects. All subjects will receive Tofacitinib 5mg twice daily for 16 weeks. After four weeks on Tofacitinib, the corticosteroid will be tapered per a pre-defined protocol (attached); once a reduction of 50% has been achieved, any further taper will be per physician discretion. The schedule for corticosteroid taper is based on 30 plus years of experience and customary practice at the Oregon Health & Science University. The experience of the investigators has consistently demonstrated an inability to taper corticosteroid dosage in many patients with sarcoidosis unless an effective, alternative immunosuppressive has been added to the patient's regimen. Furthermore, higher doses of corticosteroids have consistently been correlated with the risk of infection. (15) Throughout the trial we will be monitoring blood counts, liver function tests, lipids, renal function, and pulmonary function testing. We will also evaluate STAT-1 activity through measurement of CXCL10 levels and RNA-Seq measurement of selected transcripts (see below) before and after Tofacitinib therapy. The primary endpoint is a 50% or greater reduction in steroids with no significant decrease in pulmonary function or quality of life. After 16 weeks, subjects who meet the primary end-point will be permitted an optional one year open-label extension.

5. Study Population

a. Number of Subjects

Five subjects with histologically proven sarcoidosis with pulmonary involvement and corticosteroid dependence will be enrolled in this trial.

b. Inclusion and Exclusion Criteria

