Inclusion Criteria: Subjects age 18 and older of either sex will be included. Subjects must meet the WASOG definition of pulmonary sarcoidosis. (16) They must have histologically proven sarcoidosis, evidence of Pulmonary sarcoidosis on chest radiograph (Stage I, II, III or IV) (17), an FVC >50%, and can have concomitant extrapulmonary disease. Subjects must require 15 mg to 30 mg/day prednisone or equivalent corticosteroid to control their sarcoidosis. Dose of prednisone must be stable for 4 weeks prior to enrollment in the study. Subjects may be taking methotrexate, but may not be taking other immunosuppressive or immunomodulatory treatments (see below).

Exclusion Criteria:

- Patients taking immunomodulatory medications other than methotrexate in the two months prior to the study period will not be included. This includes but is not limited to azathioprine, cyclophosphamide, leflunomide, mycophenolate mofetil, cyclosporine, tacrolimus, and biologic medications.
- Patients requiring >30 mg/day prednisone or its equivalent.
- Pregnant or lactating women will not be included.
- Subjects with the following blood dyscrasias will not be included:
 - Hemoglobin <9g/dL or Hematocrit <30%
 - White blood cell count <3.0 K/cu mm
 - o Absolute neutrophil count <1.2 K/cu mm
 - o Platelet count <100 K/cu mm
- Subjects with an estimated GFR ≤40 ml/min
- Subjects with a total bilirubin, AST, or ALT more than 1.5 times the upper limit of normal at screening.

- Severe, progressive, or uncontrolled chronic liver disease including fibrosis, cirrhosis, or recent or active hepatitis.
- History of any lymphoproliferative disorder such as Epstein Barr virus (EBV) related lymphoproliferative disorder, history of lymphoma, leukemia, or signs and symptoms suggest of current lymphatic disease.
- Current malignancy or history of malignancy, with the exception of adequately treated or excised non-metastatic basal cell or squamous cell cancer of the skin, or cervical carcinoma in situ.
- Have or have had an opportunistic infection (e.g., herpes zoster [shingles], cytomegalovirus, Pneumocystis carinii, aspergillosis and aspergilloma, histoplasmosis, or mycobacteria other than TB) within 6 months prior to screening.
- Have a known infection with human immunodeficiency virus (HIV)

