- Study drug: Tofacitinib 5 mg twice daily will be given from week 0 to week 16 to treat sarcoidosis. Tofacitinib is FDA approved for the treatment of rheumatoid arthritis but is not FDA approved for the treatment of sarcoidosis.
- Questionnaires: At each visit, quality of life will be measured with the Saint George Respiratory
 Questionnaire (SGRQ), and assessment of involved organ systems will be measured via the WASOG
 sarcoidosis organ assessment instrument.
- Subjects should have had a chest x-ray within one year of enrollment and will have a repeat chest x-ray after the 16 weeks of treatment.

Procedures	Basel ine	Week 0*	We ek 2	Wee k 4	We ek 8	Week 12	Week 16
Informed Consent	X						
Screening labs**:	Х						
Quantiferon, HIV, HBsAg, HBcAB, HCV ab,							
Urine pregnancy test (women only)	Х						
Start study drug		Х					
End study drug							Х
Start steroid taper				Χ			
Physical Exam	Х		Χ	Χ	Χ	Х	Х
Spirometry with DLCO	X***						Х
Spirometry				Х	Х	Х	
Labs: CBC, LFT, Lipid measurement, BMP.	X***		Х	Х	Х	Х	Х
Labs: CRP	Х						Х
Labs: CXCL10 level	Х						Х
RNA Seq	Х						Х
Questionnaires: SGRQ, WASOG	Х		Х	Х	Х	Х	Х

Page 4 of 13 Revised: 7/15/2019

Adverse event reporting		Х	Χ	Х	Х	Х
Medication Reconciliation		Χ	Χ	Χ	Х	X
Chest Xray	X**					Х

^{*} There should be no more than 4 weeks between baseline and start of study drug (week 0)

***If these tests have been done within 4 weeks of baseline visit, they do not need to be repeated. HIV: human immunodeficiency virus, HBsAG: hepatitis B surface antigen, HBcAB: hepatitis B core antibody, HCV: hepatitis C virus, PFT: pulmonary function testing, CBC: complete blood count, LFT: liver function test, BMP: basic metabolic panel, CPR: C-reactive protein, SCGQ: Saint George Respiratory Questionnaire

All of the above procedures, testing, and study drug will be billed to the study. Patients and their insurance will not be billed for any of the above procedures during the 16 week study. Patients continuing on to long-term follow up may have laboratory testing billed to insurance as below under "Long term follow-up".

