Long term follow-up: Patients who do not meet the primary end point will not be followed long term. Patients who meet the primary endpoint will be continued on study drug for up to one year. During that one year they will be followed with labs (CBC, BMP, liver function panel, lipid panel) every two months, and the above questionnaires and adverse event reporting by phone every three months. A clinic visit will be required every 6 months. Labs done during the one-year extension period will be billed to the patient's insurance; study drug will be covered by Pfizer.

Voluntary withdrawal from the study: Subjects may withdraw from the intervention (study drug Tofacitinib) at any time. For subjects who choose to withdraw from the intervention we will collect the following data two weeks after withdrawal from the intervention: CBC, lipid measurement, LFT, BMP, adverse event reporting.

Treatment with Tofacitanib to be discontinued and the patient withdrawn from this study for:

- Serious infections (those requiring parenteral antimicrobial therapy or hospitalization)
- A decline in glomerular filtration rate of 33% or greater
- An increase in liver function tests (LFTs) >2.5x the upper limit of normal
- Neutrophil counts <1000 neutrophils/mm3
- Platelet counts <100,000 platelets/mm3
- Any single hemoglobin value <8.0 g/dL or one that drops ≥2 gm/dL below baseline
- Other serious or severe AEs that the investigator believes are sufficient to discontinue the medication
- Extrapulmonary disease such as uveitis with substantial worsening despite tofacitinib therapy as determined by another health care provider

7. Data and Specimens

a. Handling of Data and Specimens

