The primary endpoint will be a 50% reduction in corticosteroid requirement in at least 60% subjects (or 3/5 of the subjects) by week 16, without significant decline in their pulmonary function—defined as a >15% decline in FVC, FEV1, or DLCO relative to the baseline value.

Objective 2:

The secondary endpoints include significant decreases in of peripheral markers of STAT pathway activity using RNA sequencing and CXCL10 levels, both measured before and after 16 weeks of tofacitinib treatment.

RNA sequencing will be done using before the study drug is started, and at week 16. We will evaluate STAT1-dependent gene expression as detected in our prior publication. (18) In our previous study, we found that of the 13/18 genes known to be downstream of STAT1 were upregulated in the peripheral blood of sarcoidosis patients (WARS, A2M, CCND1, CD64, MT-1, TRH, IRF-1, PSMB9, MHC2TA, OPRM1, Pim-1, CXCL9, and CDKN1A). We expect these 13 genes to be upregulated in the blood of pre-treatment subjects, and expect this expression level to significantly decrease in post-treatment subjects. An additional 8 genes in the JAK-STAT pathway were also found to be upregulated (IFNAR1, IFNAR2, IFNAR3, JAK1, JAK2, STAT1, STAT2, and STAT3). In a rheumatoid arthritis study of synovial biopsies before and after tofacitinib, STAT1 and STAT3 were found to be significantly decreased after tofacitinib treatment. (19) Interferon alpha receptors (IFNAR) are located upstream of the JAK-STAT pathway, and whether these expression profiles are expected to change is less clear. Expression of JAK 1, JAK2, STAT1, STAT2, and STAT3 are expected to significantly decrease with tofacitinib therapy. A paired T test will be used to compare expression levels at baseline and after 16 weeks of treatment, where a p<0.05 will be considered significant.

Finally, we will be measuring peripheral CXCL10 levels. STAT1 activation leads to CXCL10 transcription, making CXCL10 a valuable peripheral marker of JAK-STAT pathway suppression. (20) Serum levels of CXCL10 have been found to be elevated in the peripheral blood of patients with sarcoidosis, and were also be found to be associated with severity and chronicity of disease. (21) Peripheral expression of CXCL10 in the rheumatoid arthritis has been found to decrease after treatment with tofacitinib. (19) A pair T-test will be used to compare peripheral CXCL10 levels before and after 16 weeks of treatment, where a p<0.05 will be considered significant.

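### Methotrexate is allowed with no requirement that it be unchanged before entry, so in this uncontrolled trial a taper helped by recently added methotrexate can count toward the 3/5

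*Combined protocol and SAP*

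**What the plan says.** Three rules in Section 5b bear on background treatment.

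- Methotrexate is permitted: "Subjects may be taking methotrexate, but may not be taking other immunosuppressive or immunomodulatory treatments (see below".
- Other agents are excluded for a period, with methotrexate exempt: "Patients taking immunomodulatory medications other than methotrexate in the two months prior to the study period will not be included".
- The only stability rule concerns the corticosteroid: "Dose of prednisone must be stable for 4 weeks prior to enrollment in the study". Sections 3 and 4 repeat the 4-week rule, again for the corticosteroid alone.

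Section 4 (Study Design) describes a single open-label arm in which every subject receives tofacitinib. "After four weeks on Tofacitinib, the corticosteroid will be tapered per a pre-defined protocol (attached"; that attachment is not in the supplied text. The same section gives the investigators' reason for expecting tapers to be informative: they have seen "an inability to taper corticosteroid dosage in many patients with sarcoidosis unless an effective, alternative immunosuppressive has been added".

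Section 8, Objective 1, sets the primary endpoint as "a 50% reduction in corticosteroid requirement in at least 60% subjects (or 3/5 of the subjects) by week 16", with a limit on decline in FVC, FEV1 or DLCO. None of the statements of the endpoint (Sections 2, 3, 4 and 8) mentions methotrexate. Section 6 schedules medication reconciliation at the post-baseline visits, but no rule uses what it records. The list of reasons for withdrawal in Section 6 does not include a methotrexate start or increase.

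**The concern.** The trial infers benefit from a successful taper. By the reasoning in Section 4, tapering often becomes possible once another effective immunosuppressive has been added. Methotrexate added or increased shortly before entry is therefore a plausible rival explanation for the outcome being counted. Without a control arm, a response in such a subject would be credited to tofacitinib.

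What is at stake is the reading of the 3/5 count. Section 2 gives the pilot's purpose as deciding whether the steroid-sparing question deserves further study. A listing can disclose a recent methotrexate change afterwards, but no analysis of five subjects can adjust for it, and eligibility cannot be revised once the subjects are enrolled.

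**Working it through.** **1. The plan's own figure.** 0.60 × 5 = 3, so the stated 3/5 is reproduced. The primary endpoint has no stated null rate, alpha or power, so there is nothing else to reproduce.

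**2. Background rules side by side (Section 5b).**

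| Agent | Status at entry | Time condition |
|---|---|---|
| Prednisone or equivalent | required, 15 to 30 mg/day | stable for 4 weeks |
| Immunomodulators other than methotrexate | excluded | two months before the study period |
| Methotrexate | allowed | none stated |

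A subject can hold prednisone constant for 4 weeks while methotrexate is started or raised in those same weeks, and still meet every criterion.

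**3. Timing.** The schedule footnote in Section 6 says: "There should be no more than 4 weeks between baseline and start of study drug (week 0". Take enrolment as the baseline visit (an assumption) and a methotrexate start 0 to 4 weeks before it.

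- Exposure when the taper begins: (0 to 4) + (0 to 4) + 4 = 4 to 12 weeks.
- Exposure at week 16: a further 12 weeks, giving 16 to 24 weeks.

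The documents do not say how fast methotrexate acts, so this shows overlap with the taper and not an effect on it.

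**4. Weight of one subject.** Exact (Clopper-Pearson) 95% intervals:

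- 3/5 = 60%, interval 14.7% to 94.7%
- 2/5 = 40%, interval 5.3% to 85.3%

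One responder is one of the three needed and moves the observed rate by 1/5 = 20 percentage points. That holds for any five-patient count and is not evidence about methotrexate.

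**5. Why no effect size follows.** Suppose the study drug is inactive, four subjects respond at rate p0, and one subject with recently changed methotrexate responds at rate q. The increase in the chance of reaching 3/5 is (q − p0) × P(exactly 2 of the other 4 respond). If q = p0 the increase is zero. The documents give neither rate, nor how many subjects would be affected. Any figure from this formula would restate the gap that was assumed, so none is used here to judge severity.

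**6. Changes on study.** The Section 5b sentence says what subjects may be taking, which reads as an entry criterion. Nothing in the supplied text permits or forbids a start or increase during the 16 weeks, or says how one counts. The attached taper protocol (Section 4) and the uploaded Data Safety Monitoring Plan form (Section 10) were not supplied and may contain a rule.

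**The case against.** The case against has several sound parts.

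- **The confounding step is inferred.** The Section 4 sentence is a rationale for the study and does not name methotrexate. Section 5b implicitly classes methotrexate with the immunosuppressives, but no section says that it works in sarcoidosis. Section 3 mentions it only as a comparator when describing tofacitinib in arthritis. This stands: the rival explanation is plausible but not demonstrated.
- **Safeguards exist.** Subjects must still require 15 to 30 mg/day at a dose unchanged for 4 weeks, the taper waits for four weeks of tofacitinib, and lung function must hold. These narrow the gap. They do not close it, because none looks at methotrexate.
- **The study is a pilot.** It is labelled hypothesis-generating, and Section 3 expects larger trials to validate the result. This lowers the consequence. A reader might infer that 3/5 is a mechanical go/no-go rule; the documents do not say so.
- **On-study changes may already be handled.** A reader might infer that the protocol lets methotrexate be added to support the taper. The supplied text is silent on this, and two documents that were not supplied could settle it. Medication reconciliation should also make such changes visible in five subjects.

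The entry gap remains after all of this. It is plain in Section 5b, and later disclosure does not remove it.

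**Conclusion.** The concern holds for entry: as written, a subject with newly started or increased methotrexate is eligible and can count toward 3/5, with no control arm to separate the effects. For changes on study, the supplied text gives no counting rule, subject to what the two documents not supplied contain.

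The size cannot be computed. The documents give no methotrexate frequency, no effect in sarcoidosis, no speed of action and no background rate of successful tapering. The only firm statement is that one such responder would be one of the three needed. A reader might infer that methotrexate would produce a false 3/5, or that the count is biased by a known amount; the documents support neither.

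The change should be made, because it is cheap and the protocol's own rationale raises the question. Confidence is medium.

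**What to change.** 1. **Section 5b.** Require that methotrexate, if used, has not been started or increased within a window before entry. The investigators set the window.
2. **Section 8, Objective 1**, unless an attached document already has a rule that can be cited. Suggested wording: *For the primary count, a subject who starts or increases methotrexate between baseline and week 16 counts as a non-responder. The count without this rule is reported alongside.* State that this is a counting rule only and does not restrict treatment.
3. **Extension wording.** Section 6 ties the extension to the endpoint: "Patients who meet the primary endpoint will be continued on study drug for up to one year". Sections 4 and 11b do the same. Reword all three so that extension entry refers to the individual response criteria without the counting rule. Otherwise the term primary endpoint would carry two meanings.
4. **Reporting.** List each subject's methotrexate status (none, stable or changed, with dates) beside the responder count and its exact 95% interval.

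The costs are protocol text and minor case report form additions for methotrexate start and change dates. Dates before entry may need outside records for referred or self-referred subjects, whom Section 5e expects to be a minority. The eligible pool becomes slightly smaller and the responder count may be lower. The effect on recruiting five subjects over two years cannot be computed from the documents.

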- Have current signs and symptoms of systemic lupus erythematosus, or severe, progressive, or uncontrolled renal, hepatic, hematologic, endocrine, pulmonary, cardiac (New York Heart Association class III or IV), neurologic, or cerebral diseases (with the exception of sarcoidosis).

Screening: Subjects will be recruited through the Oregon Health and Science University (OHSU) pulmonary, ophthalmology, rheumatology, and internal medicine clinics in addition to local community pulmonology clinics by referral. Review of OHSU medical records and Epic query will also be used to identify potential subjects. Pre-screening will take place first through chart review and then telephone interview. Subjects who are eligible for the trial after pre-screening will then be screened in person. At the screening visit subjects will receive informed consent as below. Health history and medications will be reviewed. Blood and/or urine samples will be collected, and pulmonary function testing will be done as per the baseline visit plan detailed below. Data from subjects who fail screening will be destroyed at the end of the study.

c. Vulnerable Populations

This study will not include children, pregnant women, neonates, prisoners, or decisionally impaired adults.

d. Setting

Subjects will be consented and samples will be drawn at the OHSU specialty clinics on the 3rd and 4th floors of the Physician's Pavilion. Spirometry will be performed in the pulmonary function lab in Multnomah Pavilion or Physician's Pavilion. Samples will be stored in a central repository as part of [name] laboratory.

RNA extraction and gene expression analyses will be performed by the OHSU Gene Profiling Shared Resource and the Massively Parallel Sequencing Shared Resource under the guidance of [name].

e. Recruitment Methods

Subjects will be recruited through the OHSU rheumatology, pulmonary, ophthalmology, and internal medicine clinics. Subjects referred from outside clinicians/scientists or self-referral will be allowed, but is expected to account for a minority of subjects. Postings on internet support groups for people living with sarcoidosis will also be used for recruitment. An Epic and medical record query will be used to identify potential subjects. Subjects will be contacted by phone. A copy of the phone script is attached.

f. Consent Process

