The consent process will take place in the OHSU pulmonary clinic or other appropriate OHSU clinic prior to any study procedures. [name], [name], or a member of their research team will be responsible for discussing the study and consent documents with study participants. Ample time will be provided to ask and answer questions. It will be emphasized that participation is entirely voluntary and that this will not affect ongoing clinical care. If needed, an interpreter will be provided for the consent process and subsequent study visits. There are no current plans to provide a translated consent. Written consent will be verified by study staff prior to any research procedures. The signed form will be kept in study binders.

Page 3 of 13 Revised: 7/15/2019

6. Procedures Involved

- Blood draw: A blood draw will be done at baseline and at weeks 2, 4, 8, 12, 16 (end of treatment). We estimate that the blood draw at baseline and week 16 will be approximately 15ml. We estimate that the blood draw at weeks 2, 4, 8, and 12 will be approximately 7.5ml.
- Urinalysis: Women will have a baseline urine pregnancy test.
- RNA Seq: at baseline and week 16 blood will be drawn for blood levels of CXCL10 and RNA-Seq to assess change in STAT1-dependent gene expression using a known STAT1 pathway analysis. This is genetic testing. Consent will be obtained using the attached consent from. We have chosen RNA-Seq because this is a discovery protocol and because we have expertise in the implementation of this technology with two funded, NIH RO1 proposals dependent on it. However, because this study is based on just 5 paired samples and we wish to minimize multiple statistical comparisons, we will perform a paired T test on 14 transcripts which we have previously shown to be up regulated in the blood of patients with sarcoidosis and which are downstream of STAT-1 (including STAT-1 itself).⁷ These transcripts are A2M, WARS, CCND1, STAT-1, MT-1, TRH, CD64, IRF1, PSMB9, MHC2TA, OPRM1, Pim-1, CXCL9, and CDKN1A. The thousands of additional transcripts detected by RNA Seq will be analyzed, but in all cases, changes in expression will be considered as a preliminary observation which requires validation.
- Pulmonary function testing: At baseline and at the end of treatment (week 16), we will measure spirometry with DLCO. At weeks 4, 8, and 12 we will measure spirometry only.

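### The only scheduled pregnancy test can precede the first dose by up to 4 weeks, none is scheduled afterwards, and pregnancy is not a listed reason to stop the drug

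*Combined protocol and SAP*

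**What the plan says.** **Testing.** Under Urinalysis, section 6 (Procedures Involved) states: "Women will have a baseline urine pregnancy test". In the schedule of procedures in the same section, the row beginning "Urine pregnancy test (women only" carries one mark, under Baseline. A footnote to the schedule reads: "There should be no more than 4 weeks between baseline and start of study drug (week 0". The week 0 column shows only the start of study drug.

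**Extension and withdrawal.** The long-term follow-up paragraph lists blood count, metabolic, liver and lipid panels every two months, phone contact every three months and a clinic visit every six months. The data collected two weeks after voluntary withdrawal are the same kinds of panel plus adverse events. Neither list includes a pregnancy test.

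**Exclusion.** Section 5b: "Pregnant or lactating women will not be included". Section 5c: "This study will not include children, pregnant women, neonates, prisoners, or decisionally impaired adults". Section 11a, among the study-drug risks: "Pregnancy Category C. Pregnant and breastfeeding women will not be included in this trial".

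**Stopping.** The discontinuation list in section 6 opens "Treatment with Tofacitanib to be discontinued and the patient withdrawn from this study for" and gives eight reasons. None names pregnancy. The discretionary one reads: "Other serious or severe AEs that the investigator believes are sufficient to discontinue the medication".

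**The concern.** The protocol bars pregnant women in three places and names pregnancy among the drug's risks, but section 6 checks for pregnancy once, possibly weeks before any drug is taken. A woman who conceives between that test and week 0 can start tofacitinib with the schedule followed exactly, and no scheduled test would then detect a pregnancy on treatment. Physical examinations and adverse event reporting give her chances to report one, but they are not tests. If she does report it, section 6 does not say that the drug stops.

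What is at stake is exposure of a pregnancy to a drug that the protocol means to keep from pregnant women. The trial's scientific conclusions do not depend on it.

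**Working it through.** The plan states no figure to reproduce. The check is a reading of every mention of pregnancy, followed by simple addition.

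**Inputs**
- Scheduled pregnancy tests: 1, at baseline (section 6, Urinalysis and schedule).
- Longest gap from baseline to week 0: 4 weeks (schedule footnote).
- Treatment period: 16 weeks (section 6, Study drug).
- Extension for responders: section 3 speaks of additional time up to 52 weeks, which can mean 52 weeks in total or 52 more. Sections 4, 6 and 11b describe a one-year extension, which favours 52 more.
- Hypothesised responders: 60% of 5, or 3 subjects (section 8).

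**Longest interval from the only test**

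| To | Sum | Result |
|---|---|---|
| First dose | 4 × 7 | 28 days |
| Last dose, main study | 4 + 16 | 20 weeks |
| Last dose, extension, 52 weeks as total | 4 + 16 + (52 − 16) | 56 weeks, 52 of them on drug |
| Last dose, extension, 52 weeks as additional | 4 + 16 + 52 | 72 weeks, 68 of them on drug |

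Pregnancy tests scheduled after baseline: 0. Discontinuation reasons naming pregnancy: 0 of 8.

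**Does a waiver widen the 4 weeks?** Another footnote lets screening labs or a chest x-ray from the past year stand. It is attached to the screening-labs and chest x-ray rows. The pregnancy test has its own row with an unmarked X, so the fair reading is that the waiver does not apply and 4 weeks is the limit.

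**How the protocol treats its other exclusions**

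| Item | Exclusion (5b) | Scheduled at weeks 2, 4, 8, 12, 16 | Stopping rule (6) |
|---|---|---|---|
| Hemoglobin | yes | yes | yes |
| Neutrophils | yes | yes | yes |
| Platelets | yes | yes | yes |
| Renal function | yes | yes | yes |
| Liver tests | yes | yes | yes |
| Pregnancy | yes | no | no |

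The gap is therefore measured against the protocol's own practice: the five laboratory exclusions are rechecked on treatment and carry stopping rules, and pregnancy has neither.

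**The case against.** The textual facts are not in dispute. The objections concern weight.

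- **The provisions may sit elsewhere.** Section 10 refers safety monitoring to a separate Data Safety Monitoring Plan, section 13 refers to a pharmacy manual, and the consent form was not available. Any of these could require contraception, testing or stopping. This stands as a limit: the finding covers section 6 and its schedule only. Nothing supplied shows that those documents do cover it.
- **A known pregnancy is already barred.** Sections 5c and 11a can be read as applying throughout the study, and without a definition of adverse event in the supplied text, the discretionary bullet cannot be ruled out as covering pregnancy. This largely stands for the stopping bullet, which is mostly clarification. It does not help with an undetected pregnancy, because a bar cannot be applied without a test.
- **Every interval is an upper bound.** True. Baseline and week 0 may fall close together, the typical gap is unknown, and the number of women of child-bearing potential is not stated.
- **The essential fix still leaves no test on treatment.** Also true. The required test closes the gap before first dose only; the 20-, 56- and 72-week intervals are shortened only by the optional repeats. The pre-dose test is the part for which the plan's own exclusion makes the strongest case. How often to repeat it is a judgement for the sponsor.

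**Conclusion.** The concern holds. As written, section 6 allows up to 28 days between the only pregnancy test and the first dose. Test to last dose is up to 20 weeks in the main study and, for responders who enter the extension, up to 56 weeks, or 72 on the better-supported reading. The extension figures would apply to about 3 subjects of either sex if the hypothesised response is seen.

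The protocol does not permit dosing in a known pregnancy, and this finding does not say so. The gap is that nothing scheduled after baseline would reveal one and section 6 gives no explicit instruction to stop. Women of child-bearing potential could number 0 to 5, and the documents give no fetal-risk figure, so the harm cannot be sized.

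This should be corrected, with medium confidence, because documents not supplied may already fill the gap. Endpoints, sample size and analysis are unaffected.

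**What to change.** **Essential**
1. Add a urine pregnancy test for women of child-bearing potential immediately before the first dose, at week 0 or at dispensing. The test-to-dose interval then falls from up to 28 days to 0.
2. Add *confirmed pregnancy* to the discontinuation list in section 6.

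If the consent form, Data Safety Monitoring Plan or pharmacy manual already provides for this, a cross-reference in section 6 is enough.

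**Advisable.** Repeat urine tests at existing visits, including week 16 before the extension, with the frequency left to the sponsor.

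**Cost.** The essential part is 1 test per woman, so 0 to 5 tests in the trial, plus one line of text. Because week 0 lists only the start of drug, a brief contact at dispensing may be needed.

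Optional repeats per woman:
- Main study: 1 (week 16 only) to 4 (weeks 4, 8, 12 and 16).
- Extension at six-monthly visits: 36/26, or 1 whole visit, to 52/26 = 2.
- Extension at two-monthly labs: 8.3/2, or 4 whole tests, to 12/2 = 6.

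The most per woman is 1 + 4 + 6 = 11, so 5 × 11 = 55 for the trial. Adding week 2 makes it 12 and 60. Both ceilings assume that all five subjects are women of child-bearing potential and that all enter the extension. With 3 of them in the extension, and without week 2, the total is 5 × (1 + 4) + 3 × 6 = 43.

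Extension labs are billed to the patient's insurance, so the sponsor must decide who pays for any extension tests.
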